7.3. Lost to Follow up

A subject will be considered lost to follow-up if he/she repeatedly fails to call in for required visits and is unable to be contacted by the clinical investigational site.

The following actions must be taken if a subject fails to call in for a required clinical investigation visit or complete the questionnaire:

- The site must attempt to contact the subject and reschedule the missed assessments as soon as possible, counsel the subject on the importance of maintaining the assigned visit schedule and ascertain whether the subject wishes to and/or should continue in the clinical investigation.
- Before a subject is deemed lost to follow-up, the investigator or designee must make every effort to regain contact with the subject (where possible, at least 3 telephone calls

- plus additional methods such as SMS/email). These contact attempts should be documented in the subject's medical record.
- Should the subject continue to be unreachable, he/she will be considered to have withdrawn from the clinical investigation.

8. Clinical Investigation Assessments and Procedures

- Clinical investigation procedures and their timing are summarized in the SoA. Procedures will be performed via telehealth or phone calls.
- Waivers or exemptions are not allowed.
- Adherence to the clinical investigation design requirements, including those specified in the SoA, is essential and required for conduct of the clinical investigation.
- All screening evaluations must be completed and reviewed to confirm that potential subjects meet all eligibility criteria.

8.1. Pre-screening and Screening/Baseline Assessments

Planned timepoints for all pre-screening and screening/baseline assessments are provided in the SoA.

8.1.1. Pre-screening assessment

Eligibility at pre-screening will be assessed by GAD-7 and patient reported medical information. Upon registering at the investigation landing page, subjects will be prompted to complete the prescreen GAD-7 questionnaires. Subjects are required to have a GAD-7 composite score of ≥5 at both pre-screening and baseline to be eligible. If the GAD-7 composite score at pre-screening is <5, no further assessments will be performed.

Subjects will be asked for additional self-reported information relevant to assess eligibility.

If the subject is confirmed eligible per pre-screening assessments, the consent form for support with medical records (CT scan, cf. Section 8.1.3) can be obtained.

The information collected at the pre-screening assessment is done prior to obtaining informed consent, and the data obtained will consequently not be included in the clinical database. It will only be used for the purpose of assessing eligibility criteria.

8.1.2. Screening/Baseline assessments

Subjects confirmed eligible based on the pre-screening assessments will be requested to provide a CT scan report confirming their PF diagnosis or provide their physician information in order for Curebase to request the report on their behalf. Once received, a video call with the site staff/Clinical Research Coordinator (CRC) will take place to obtain consent and conduct the baseline visit procedures. The Principal Investigator (PI) will then evaluate eligibility after informed consent has been obtained and baseline visit has been completed.

8.1.2.1. Demographics

Demographic and baseline characteristics will be obtained. The following information will be collected:

- Age
- Race and ethnicity
- Sex

8.1.2.2. Medical History

All current medical conditions and relevant previous medical conditions should be recorded.

For the pilot phase, subjects can be included based on self-reported IPF diagnosis. If available, medical history information may also be recorded for the pilot phase.

For the pivotal phase, the following information is required:

- PF diagnosis confirmation (self-reported)
- Date of PF diagnosis (self-reported, approximate/incomplete date is accepted if not known)
- CT report (no more than 5 years old). A non-high-resolution CT may be sufficient to confirm the diagnosis. Inclusion criteria 5 will always be assessed based on investigator judgement and should the CT scan report not be sufficient to confirm the diagnosis, an HRCT scan report can be requested to confirm eligibility.
- Other relevant diseases reported by the subject.

8.2. Efficacy Assessments

Planned timepoints for all efficacy assessments are provided in the SoA.

8.2.1. General Anxiety Disorder-7

Anxiety severity will be assessed by GAD-7 by the subject using an electronic diary on their own smartphone, tablet device or computer.

The GAD-7 questionnaire includes the following questions (paper version displayed):

GAD-7 Anxiety

Over the last two weeks , how often have you been bothered by the following problems?		Several days	More than half the days	Nearly every day
Feeling nervous, anxious, or on edge	0	1	2	3
Not being able to stop or control worrying	0	1	2	3
Worrying too much about different things	0	1	2	3
Trouble relaxing	Ö	1	2	3
Being so restless that it is hard to sit still	0	1	2	3
Becoming easily annoyed or irritable	0	ì	2	3
Feeling afraid, as if something awful might happen	Ö	1	2	3

	Column totals	+	+ + =
			Total score
	olems, how difficult have the along with other people?	y made it for you to	do your work, take care of
Not difficult at all	Somewhat difficult	Very difficult	Extremely difficult

Source: Primary Care Evaluation of Mental Disorders Patient Health Questionnaire (PRIME-MD-PHQ). The PHQ was developed by Drs. Robert L. Spitzer, Janet B.W. Williams, Kurt Kroenke, and colleagues. For research information, contact [name] at [contact]. PRIME-MD® is a trademark of Pfizer Inc. Copyright® 1999 Pfizer Inc. All rights reserved. Reproduced with permission

The response scores of the first 7 questions are added to create a composite score (range 0-21), with higher scores indicating a higher level of anxiety.

Composite scores of \leq 4, 5-9, 10-14, and \geq 15 represent minimal, mild, moderate, and severe anxiety, respectively.

8.2.2. Kings brief interstitial lung disease questionnaire

PF HRQoL will be assessed by K-BILD by the subject using an electronic diary on their own smartphone, tablet device or computer.

The K-BILD questionnaire includes the following questions (paper version displayed):

- In the last 2 weeks, I have been short of breath climbing stairs or walking up an incline or hill.
- 1. Every time
- 2. Most times
- 3. Several Times
- 4. Sometimes
- 5. Occasionally
- 6. Rarely
- 7. Never
- In the last 2 weeks, because of my lung condition, my chest has felt tight.
- 1. All of the time
- 2. Most of the time
- 3. A lot of the time
- 4. Some of the time
- 5. A little of the time
- 6. Hardly any of the time
- 7. None of the time
- 3. In the last 2 weeks have you worried about the seriousness of your lung symptoms?
- 1. All of the time
- 2. Most of the time
- 3. A lot of the time
- 4. Some of the time
- 5. A little of the time
- 6. Hardly any of the time
- 7. None of the time
- 4. In the last 2 weeks have you avoided doing things that make you short of breath?
- 1. All of the time
- 2. Most of the time
- 3. A lot of the time
- 4. Some of the time
- 5. A little of the time
- 6. Hardly any of the time
- 7. None of the time

[figure not shown]
- 5. In the last 2 weeks have you felt in control of your lung condition?
- 1. None of the time
- 2. Hardly any of the time
- 3. A little of the time
- 4. Some of the time
- 5. A lot of the time
- 6. Most of the time
- 7. All of the time
- 6. In the last 2 weeks, have your lung symptoms made you feel annoyed or down?
- 1. All of the time
- 2. Most of the time
- 3. A lot of the time
- 4. Some of the time
- 5. A little of the time
- 6. Hardly any of the time
- 7. None of the time
- In the last 2 weeks, I have felt the urge to to inhale deeply and frequently known as "air hunger."
- 1. All of the time
- 2. Most of the time
- 3. A lot of the time
- 4. Some of the time
- 5. A little of the time
- 6. Hardly any of the time
- 7. None of the time
- In the last 2 weeks, my lung condition has made me feel anxious.
- 1. All of the time
- 2. Most of the time
- 3. A lot of the time
- 4. Some of the time
- 5. A little of the time
- 6. Hardly any of the time
- 7. None of the time

- 9. In the last 2 weeks, how often have you experienced "wheezing" or whistling sounds from your chest?
- 1. All of the time
- 2. Most of the time
- 3. A lot of the time
- 4. Some of the time
- 5. A little of the time
- Hardly any of the time
- 7. None of the time
- 10. In the last two weeks how much of the time have you felt your lung disease is getting worse?
- 1. All of the time
- 2. Most of the time
- 3. A lot of the time
- 4. Some of the time
- 5. A little of the time
- Hardly any of the time
- 7. None of the time
- 11. In the last 2 weeks has your lung condition interfered with your job or other daily tasks?
- 1. All of the time
- 2. Most of the time
- 3. A lot of the time
- 4. Some of the time
- 5. A little of the time
- Hardly any of the time
- 7. None of the time
- 12. In the last 2 weeks have you expected your lung symptoms to get worse?
- 1. All of the time
- 2. Most of the time
- 3. A lot of the time
- 4. Some of the time
- 5. A little of the time
- 6. Hardly any of the time
- 7. None of the time

[figure not shown]
- 13. In the last 2 weeks, how much has your lung condition limited you carrying things, for example, groceries?
- 1. All of the time
- 2. Most of the time
- 3. A lot of the time
- 4. Some of the time
- 5. A little of the time
- 6. Hardly any of the time
- 7. None of the time
- 14. In the last 2 weeks, has your lung condition made you think more about the end of your life?
- 1. All of the time
- 2. Most of the time
- 3. A lot of the time
- 4. Some of the time
- 5. A little of the time
- 6. Hardly any of the time
- 7. None of the time
- 15. Are you financially worse off because of your lung condition?
- 1. A significant amount
- 2. A large amount
- 3. A considerable amount
- 4. A reasonable amount
- 5. A small amount
- 6. Hardly at all
- 7. Not at all

Thank you for completing this questionnaire.

Scores will be calculated for each domain (breathlessness and activities, chest symptoms and psychological) and for the total questionnaire. The K-BILD domain and total scores ranges are 0-100; 100 represents the best health status.

PAIN / DISCOMFORT I have no pain or discomfort I have slight pain or discomfort I have moderate pain or discomfort I have severe pain or discomfort I have extreme pain or discomfort ANXIETY / DEPRESSION I am not anxious or depressed I am slightly anxious or depressed I am moderately anxious or depressed I am severely anxious or depressed

I am extremely anxious or depressed

[figure not shown]
8.2.5. Hamilton anxiety rating scale

The HAM-A scale will be used to assess clinician-rated signs and symptoms of anxiety. Ratings will be performed by clinician-based interviews with the subject. The clinician will be independent to the site staff conducting the investigation and blinded to the subject's treatment assignment. The subject will be instructed not to mention their investigational treatment during the interviews. A structured interview guide for the HAM-A scale (SIGH-A; past week recall) will be used to complete the assessments.

HAM-A will be completed no more than 2 days after the subject has completed the patient-reported questionnaires. The HAM-A will be completed electronically; the paper version is displayed below.

Hamilton Anxiety Rating Scale (HAM-A) Below is a list of phrases that describe certain feeling that people have. Rate the patients by finding the answer which best describes the extent to which he/she has these conditions. Select one of the five responses for each of the fourteen questions.						
					0 =	Not present,
ľ	Anxious mood	0 1 2 3 4	8	Somatic (sensory)	0 1 2 3 4	
Worries, anticipation of the worst, fearful anticipation, irritability.			Tinnitus, blurring of vision, hot and cold flushes, feelings of weakness, pricking sensation.			
2 Fee	Tension lings of tension, fatigability, st	0 T 2 3 4 artle response, moved to tears	9	Cardiovascular symptoms	0 1 2 3 4	
easily, trembling, feelings of restlessness, inability to relax.				Tachycardia, palpitations, pain in chest, throbbing of vessels, fainting feelings, missing beat.		
3	Fears	0 1 2 3 4	. 10	Respiratory symptoms	0 1 2 3 4	
Of dark, of strangers, of being left alone, of animals, of traffic, of crowds.			T .	Pressure or constriction in chest, choking feelings, sighing, dyspnea.		
4	Insomnia	0 1 2 3 4	11	Gastrointestinal symptom	s 0 1 2 3 4	
Difficulty in falling asleep, broken sleep, unsatisfying sleep and fatigue on waking, dreams, nightmares, night terrors.			abdo	Difficulty in swallowing, wind abdominal pain, burning sensations, abdominal fullness, nausea, vomiting, borborygmi, looseness of bowels, loss of weight, constipation.		
5	Intellectual	0 1 2 3 4				
Difficulty in concentration, poor memory.		12	Genitourinary symptoms	0 1 2 3 4		
6	Depressed mood	0 1 2 3 4	men	Frequency of micturition, urgency of micturition, amenorrhea, menorrhagia, development of frigidity, premature ejaculation, lo: libido, impotence.		
	s of interest, lack of pleasure rnal swing.	in hobbies, depression, early w	aking,	o, impotence.		
ului	nai swing.		13	Autonomic symptoms	0 1 2 3 4	
7 Pain	Somatic (muscular) as and aches, twitching, stiffne	ular) 0 1 2 3 4 ng, stiffness, myoclonic jerks, grinding of		Dry mouth, flushing, pallor, tendency to sweat, giddiness, tension headache, raising of hair.		
teeth, unsteady voice, increased muscular tone.			14	Behavior at interview	0 1 2 3 4	
			Fidgeting, restlessness or pacing, tremor of hands, furrowed brow, strained face, sighing or rapid respiration, facial pallor, swallowing, etc.			

HAM-A is a 14-item questionnaire rating the intensity of psychic and somatic anxiety on a 5-point severity scale. Each item ranging from 0 (not present) to 4 (very severe) will be summed up to give a total possible score of 0 to 56, where lower scores indicate less anxiety.

8.2.7. Video interview to evaluate functionality (applicable for pilot phase only)

In the pilot phase, subjects will be interviewed by delegated Alex Therapeutics staff following a separate semi-structured interview guide. Topics can include:

1. Is the product helpful?

- a. What new learnings have the product provided?
- b. Has the product led to any real change in everyday life?
- c. Has it affected your overall anxiety and mood?

2. Is the product intuitive?

a. Was the product able to instinctively understand your mood?

3. Is the product engaging?

- a. Do people stay for the whole program?
- b. Where do people drop-off?
- c. Where is motivation lacking?
- d. Is there any particular content that is hard to understand and/or bothersome

4. Is it specific enough to IPF patients?

- a. Do IPF patients recognize themselves in content and examples?
- b. Is there something that is not addressed?

Video interviews will be transcribed, and outcomes will be summarized in a separate report.

8.3. Safety Assessments

Planned timepoints for all safety assessments are provided in the SoA (see Section 1.3).

8.4. Adverse Events, Serious Adverse Events, and Other Safety Reporting

The definitions and reporting requirements for AEs, ADEs, SAEs, and SADEs can be found in Appendix 2 (see Section 10.2).

AEs will be reported by the subject and will be classified as AEs, ADEs, SAEs, and SADEs according to the definitions provided in Section 10.2. ADEs and SADEs can only occur in the dCBT-PF group as there are no intervention in the control group. All ADEs, SAEs and SADEs should be reported in the CRF. Aes, not fulfilling the definition of an ADE, SAE, and SADE, should only be reported if they are related to a psychological disorder or a procedure of the clinical investigation.

The investigator and any qualified designees are responsible for detecting, documenting, and recording events that meet the definition of an AE, ADE, SAE, or SADE. They further remain responsible for following up on AEs, ADEs, SAEs, or SADEs.

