2.3.3. Overall Benefit Risk Conclusion

The overall benefit risk balance is considered positive. This is based on the consideration that none, or a limited number of, ADEs are expected using dCBT, the virtual nature of the clinical investigation and potential benefits in treating anxiety with dCBT.

3. Objectives, Endpoints, and Estimands

[figure not shown]
Pilot investigation – Part 1:

Objectives	Endpoints
Primary	
To evaluate the functionality of dCBT-PF in patients with IPF	Subjects feedback on functionality and experience of the dCBT-PF at Week 4
Safety	
To evaluate the safety of dCBT-PF in patients with IPF	AEs, ADEs, SAEs, SADE and device deficiencies which could lead to an ADE or SADE

Pivotal investigation – Part 2:

Objectives	Endpoints
Primary	
To evaluate the efficacy of dCBT-PF versus control on patient-reported anxiety symptoms in patients with PF	Change from baseline in anxiety symptom severity assessed by GAD-7 at Week 9
Key secondary	
To evaluate the efficacy of dCBT-PF versus control on clinician-reported anxiety symptoms in patients with PF	Change from baseline in anxiety symptom severity as assessed by Hamilton anxiety rating scale (HAM-A) at Week 9
To evaluate the efficacy of dCBT-PF versus control on patient-reported health-related quality of life (HRQoL) in patients	Change from baseline in HRQoL assessed by K-BILD psychological domain score at Week 9
with PF	Change from baseline in HRQoL assessed by K-BILD total score at Week 9

Safety	
To evaluate the safety of dCBT-PF versus control in patients with PF	AEs, ADEs, SAEs, SADEs and device deficiencies which could lead to an ADE or SADE

Primary Estimand:

The change from baseline to Week 9 in GAD-7 scores, assessed for the intention-to-treat population with treatment as randomised, independent of treatment withdrawal or major deviations according to the treatment policy, with withdrawals from the clinical investigation prior to Week 9 not possible to follow-up being imputed using multiple imputation including their last known assessment. The difference between treatments with 95% confidence intervals from ANCOVA adjusting for stratification will be estimated.

Key Secondary Estimands:

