9.3.4. Safety Analyses

Safety analysis will be based on the safety set.

AEs will be analyzed using quantitative and qualitative measures. AEs will be summarized by treatment group for all AEs, ADEs, SAEs, SADEs (unanticipated SADE (USADE), or anticipated SADE (ASADE)), deaths, AEs leading to discontinuation of dCBT-PF or to withdrawal from investigation, and device deficiencies. AEs will be coded using the Medical Dictionary for Regulatory Activities (MedDRA) and summarized by system organ class and preferred term for each treatment group. ADEs and SADEs only applies to the dCBT-PF therapy group.

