10.2. Appendix 2: AEs, ADEs, SAEs and SADEs: Definitions

10.2.1. Definition of AE

AE Definition

An AE is any untoward medical occurrence, unintended disease or injury, or untoward clinical signs (including laboratory finding) in subjects (i.e., participants in the clinical investigation), users or other persons, whether or not related to the investigational medical device and whether or not anticipated or unanticipated.

Notes:

 Includes events related to the investigational medical device or the comparator, and the procedures involved

Comparator is used in the control group and can be:

- Medical device
- Therapy (e.g., active treatment, normal clinical practice)
- Placebo
- No treatment

Lack of efficacy per se will not be reported as an AE or SAE. Such instances will be captured in the efficacy assessments.

AEs, not fulfilling the definition of an ADE, SAE, and SADE, should only be reported if they are related to a psychological disorder or a procedure of the clinical investigation.

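### By-arm AE tables in 9.3.4 are not like for like: some non-serious events can be recorded only on dCBT-PF, and 10.2.5 contradicts the ADE definition (minor)

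*Combined protocol and SAP*

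**What the plan says.** Section 8.4 sets the recording rules for both arms:

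- "All ADEs, SAEs and SADEs should be reported in the CRF".
- Any other AE "should only be reported if they are related to a psychological disorder or a procedure of the clinical investigation". Section 10.2.1 repeats this filter.
- "ADEs and SADEs can only occur in the dCBT-PF group as there are no intervention in the control group".

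Section 10.2.2 ties an ADE to use of the investigational device. It extends this to a comparator only where the comparator is itself a medical device. Section 6.3 says that the control group receives no treatment.

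Section 10.2.5 gives one causality scale covering device or procedure, and classes every AE rated possible, probable or causal as an ADE. It also asks for a pre-existing condition to be reported if it becomes more severe.

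On analysis, 9.3.4 says "AEs will be summarized by treatment group for all AEs, ADEs, SAEs, SADEs" and lists further categories. It adds tables by system organ class and preferred term for each arm, and notes that "ADEs and SADEs only applies to the dCBT-PF therapy group". The Part 2 safety objective in Section 3 is comparative, dCBT-PF versus control.

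**The concern.** A by-arm AE table can be read as a comparison only if an event of a given kind has the same chance of being entered in both arms. Here one kind of event enters through the device-relatedness route, which is closed to control. If the same event occurs equally often in both arms, some of the dCBT-PF events reach the table and none of the control events do. Anyone reading the overall row or a non-psychological preferred-term row, including the data monitoring committee that reviews safety data under 10.1.5.1, could take a product of the recording rule for a difference between arms.

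The second issue is one of definition. If 10.2.5 is followed literally, the ADE count includes procedure-related events, and a procedure-related event in a control subject is an ADE under one section and cannot be an ADE under another.

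**Working it through.** The plan states no AE rate, so there is no figure to reproduce. The check traces each event type through 8.4, 10.2.1, 10.2.2 and 10.2.5.

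| Event type | dCBT-PF | Control |
|---|---|---|
| SAE, including death | reported | reported |
| Non-serious, psychological | reported | reported |
| Non-serious, procedure-related | reported | reported |
| New, non-serious, neither of the above, rated at least possibly device-related | reported as ADE | no such route |
| New, non-serious, neither of the above, rated not related | not reported | not reported |

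Only the fourth line differs by arm. The comparator clause in 10.2.2 does not open it for control, because the comparator is no treatment. The general duty in 8.4 to record events meeting the AE definition does not open it either: the explicit filter governs what is reported, and 8.4.1 asks only for relevant AEs in the CRF. Worsened pre-existing conditions are left out, because 10.2.5 does not say whether that rule is subject to the 8.4 filter.

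The note in 9.3.4 that ADEs apply only to dCBT-PF explains the ADE row. It does not take ADEs out of the overall row or the preferred-term rows.

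**Scale.** Maximum enrolment is 250 with 1:1 allocation (Synopsis): 250 / 2 = 125 per arm. One subject is 1 / 125 = 0.8 percentage points. Recruitment may stop earlier, at the end of July 2023, so 125 is a ceiling and 0.8 points a floor.

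The expected excess in the overall row is 125 × p × q × (1 − r), taking the three quantities as independent. Here p is the proportion of subjects with such an event, q the share of those rated at least possibly device-related, and r the share who already have another reportable AE. None of the three is in the documents. At assumed low values p = 5%, q = 10% and r = 20%, the result is 125 × 0.05 × 0.10 × 0.80 = 0.50 subject, and 0.50 / 125 = 0.4 percentage points.

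**Definition of an ADE.**

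- Under 10.2.2, only a relationship to device use makes an AE an ADE.
- Under 8.4 and 10.2.1, procedure-related AEs can fall outside the ADE definition; 10.2.1 reads "AEs, not fulfilling the definition of an ADE, SAE, and SADE, should only be reported if they are related to a psychological disorder" and continues with procedure-related ones.
- Under 10.2.5, a relationship to device or procedure, rated possible or higher, makes an AE an ADE.
- Under 8.4 and 9.3.4, there are no ADEs on control.

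The third statement conflicts with the other three. It does not add to the imbalance above, because procedure-related AEs are recordable in both arms on either reading. It changes the classification and the ADE count.

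**The case against.** The strongest reply is that the affected class is nearly empty. Section 2.3.1 names one residual risk, negative wellbeing or distress. That is psychological, so it is reportable in both arms, and Table 2 schedules a question on it at every post-baseline visit. The section anticipates no other source of ADEs, and 2.3.3 expects that "none, or a limited number of, ADEs are expected using dCBT". This stands, and it is the main reason for rating the point minor.

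Second, the rule works against the device: it can add events to dCBT-PF but cannot hide harm. This also stands. A reader might infer that the safety evaluation is biased in the product's favour or invalid as a whole; the documents support neither.

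Third, a reader might infer a large imbalance. Assumed values of p = 20%, q = 50% and r = 10% give 125 × 0.20 × 0.50 × 0.90 = 11.25 subjects, or 9 percentage points. Nothing in the documents supports attributing half of such events to the app, and 2.3.1 and 2.3.3 point the other way. Nor should a split such as 6 versus 0 be read through a significance test, because 9.3.4 plans none for safety.

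Fourth, Section 9 leaves technical detail to the SAP, and the separate ADE row already makes much of the excess visible. The SAP could indeed restrict or footnote the tables, and no table specifications were available to check. It cannot recover control events that were never entered, and 9.3.4 as written does not separate the rows.

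Finally, 10.2.5 may be meant to concern device causality only. That reading is reasonable, but it is not what the section says.

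**Conclusion.** Wrong as written, minor. The overall AE row and the non-psychological system organ class and preferred-term rows in 9.3.4 are not like for like between arms, and the recording rule can only add events to dCBT-PF. The size cannot be derived from the documents. Given 2.3.1 and 2.3.3 it is probably small, at 0.8 percentage points or more for each additional subject. The tables are descriptive, so the risk is a misleading summary and not a wrong test.

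A reader might infer that every other row is fully comparable. That goes too far. SAEs, deaths, psychological AEs and procedure-related AEs do fall under the same reporting rule in both arms. But 6.4 has site staff contact dCBT-PF users whose compliance is low, with no matching contact described for control, so opportunity for detection and exposure to procedures can differ.

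The conflict between 10.2.5 and the other ADE statements is a separate drafting fault. It does not depend on any assumed rate.

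**What to change.** **Tables (9.3.4, or the SAP table specifications).**

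- Compare arms on categories reportable under the same rule in both: SAEs including deaths, psychological-disorder AEs, and procedure-related AEs, each counted regardless of device causality.
- Show the remaining ADEs for dCBT-PF only.
- Footnote the 8.4 reporting rule and the compliance contacts that only dCBT-PF subjects can receive.
- Do not use a row of AEs excluding ADEs. It would remove psychological ADEs from dCBT-PF alone and tilt the table the other way.

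**Definitions.** Reconcile 8.4, 10.2.1, 10.2.2 and 10.2.5. Record device and procedure causality separately, class an AE as an ADE on the device rating only, and state whether the pre-existing-condition rule is subject to the 8.4 filter.

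**Cost.** A wording amendment, with IRB approval before implementation (10.1.1). Two CRF fields may be needed if not already captured: a separate causality rating, and a flag for relation to a psychological disorder that also covers ADEs, because 8.4 has ADEs reported without applying that criterion. No extra visits are needed.
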